WHO	World Health Organization

PROTOCOL SUMMARY

Title:	Family Intervention With Caregivers Of Children With Dental Needs
Précis:	The study is a multi-site, double blind, parallel arm, community-based randomized controlled trial (phase III RCT) to evaluate the effectiveness of new referral approaches to increase receipt of dental care among inner-city urban and rural elementary school children who were screened at school and have restorative treatment needs. The study has 5 arms: The experimental intervention is the use of a theoretically driven CSM referral letter alone, the CSM letter plus a Dental Information Guide, a reduced CSM referral letter alone, or a reduced CSM referral letter plus a reduced Dental Information Guide. The control strategy is the use of a modified standard referral letter. All RCT participating K-4 grade children will receive a screening at the beginning of the school year and at the study end point 7 months later to determine if the child received dental care.
Objective	
Primary: To evaluate the effectiveness of experimental (new) versus standard referral approaches given to parents/caregivers in increasing receipt of dental care among their children in grades K-4.
 
Secondary: To assess changes in parent/caregiver illness representation/perception and behavioral intention between enrollment (beginning of school year), 2-week and 7-month follow-up (end of school year) to understand the underlying mechanisms of the new vs. standard referral approach that result in receipt of dental care.

Population:	Population information: sample size=660 caregivers to be randomized; children will be both male and female, grades K-4; inner city African Americans (Bedford and E Cleveland, OH) and rural Whites and Hispanics (Cowlitz and Lewis counties, Washington State).
Phase:	III
Number of Sites:	
(1) East Cleveland City School District (ECCSD, Cleveland, OH), and Bedford City School District (BCSD, Bedford, OH).
 
(2) Cowlitz County (CCSD, WA), and Lewis County (LCSD, WA).

Description of Intervention:	The experimental intervention is the use of a theoretically driven CSM referral letter alone or the letter plus a dental information guide. The control strategy is the use of a modified standard referral letter.
Study Duration:	10 months
Subject Participation Duration:	1 year

Estimated Time to Complete Enrollment: 3 months

SCHEMATIC OF STUDY DESIGN

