Washington Sites: These sites will use the same recruitment approach as ECCSD. The study intends to recruit 1452/1708 K-4 children (85%). In a recent screening with a similar rural population (Jefferson and Morrow Counties, OR), 85% of families agreed to participate with only a single notice home and no personal contact or follow-up. In an earlier study with a similar rural population, UW investigators recruited 76% of eligible families (Weinstein, Spiekerman & Milgrom 2009). Based on 28% caries rate, we expect that 407/1452 recruited children will be screened positive for untreated caries. 5% of the children who are positive will be excluded because of emergent needs. Further 10% will be caregivers with multiple children. Thus, an available pool of 348 caregivers will be eligible for randomization.

Due to lower than expected enrollment in both the Ohio and Washington sites, we plan a second year of recruitment to include Bedford School District and East Cleveland School District (only KG and perhaps other grades if they did not enroll in the first year). For the Bedford School District, 1274 KG-4th grade children were enrolled during 2015-2016 school year in four elementary schools; 80% Black; 67% economically disadvantaged eligible for free/reduced cost school lunch program. Bedford is quite similar to East Cleveland. Using our experience from the first year of recruitment we expect that out of the 1274 Bedford school children, about 764 will receive baseline screening (60% participation rate). Of 764 children, about 267 caregivers will be randomized (taking into account 30% multiple children and 50% caries rate). Similarly we expect about 50 caregivers will be randomized in East Cleveland. Between Bedford and East Cleveland School Districts, we expect to screen about 950 children in 2016-2017 school year. Of the 950 screened we expect to randomize 317 caregivers. So we can meet our recruitment goal of 258 caregivers that is necessary to complete the study.

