12.2 Sample Size Considerations

The primary aims are to compare dental care receipt among the five intervention groups, overall and separately for each study site (Ohio and Washington).

The five intervention groups are:

Arm 1: CSM referral letter alone (N=204)

Arm 2: CSM referral letter + DIG (N=204)

Arm 3: Reduced CSM referral letter alone (N=24)

Arm 4: Reduced CSM referral letter + DIG (N=24)

Arm 5: Modified Standard letter (N=204)

The utilization will be defined as evidence of dental care through restorations or extractions at the final study visit exam that was previously not found during the baseline exam. All changes will be recorded on a tooth level using ICDAS criteria and then dichotomized at the caregiver level as having obtained or not obtained dental care for their child/children.

There are three treatment comparisons to assess the overall CSM referral letter and DIG: CSM referral letter alone versus standard letter (Arm 1 vs Arm 5), CSM referral letter plus DIG versus standard letter (Arm 2 vs Arm 5), and CSM referral letter alone versus CSM referral letter plus DIG (Arm 1 vs Arm 2). As described below we address the issue of multiple testing, both multiple comparisons and multiple sites, using a gatekeeper approach. By specifying a sequence of tests, this approach will allow for the use of a nominal 0.05 alpha level for each test while maintaining a 0.05 family-wise alpha level for the six tests (three at each study site).

An additional comparison will be conducted to assess the effect of the targeted component (e.g., the ‘timeline’ text): CSM referral letter with and without DIG versus reduced CSM referral letter with and without DIG (Arm 1, 2 vs Arm 3, 4).

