The sample size was calculated with the following assumptions for the overall effect of the intervention letter: 19% utilization rate for standard letter (Nelson et al. 2012), 37% rate for CSM referral letter alone (based on Medicaid utilization among children: GAO-08-1121, 2008), 57% rate for CSM referral letter + DIG (based on 57% who reported that they took their child to the dentist or had an appointment after receiving the CSM referral letter + DIG in the R34 study). Then, using a two-sided test for equal proportions (namely, a Z test with pooled variance), we find that a sample size of 102 per intervention group per site (thus, 306 subjects per site) will provide 80% power to detect rate differences of 19% versus 37% (as expected for Arm 5 vs Arm 1) or 37% versus 57% (as expected for Arm 1 vs Arm 2) for each site, and 98% power for each of these comparisons using the

combined sample. As siblings (with the same caregiver) may be included in the study, a conservative approach will be to consider the required sample sizes as referring to the number of caregivers. Somewhat greater power will be expected if within-caregiver correlation is less than 1.

For the Ohio site with a total of 889 potential children, we expect 86% to participate (Nelson & Milgrom 2012), with 56% receiving a referral and 5% excluded for emergent needs. From previous [name] study in ECCSD elementary schools we expect 10% of caregivers to have multiple (usually two) children. Thus, an estimated total of 366 caregivers will be available for randomization to the five groups. For the Washington sites, with a total of 1704 potential children, we expect 85% participation (based on 2013 screenings in both districts), with 28% receiving a referral, 5% exclusions for emergent needs, and a 10% reduction in the corresponding number of caregivers due to inclusion of siblings. A total of 347 caregivers will be available for randomization. Even with 5% out of school transfers, the available sample will be adequate for testing the proposed hypothesis. Thus, we expect to randomize 330 caregivers/site to the five study arms to account for any drop-outs at randomization and maintain the required power for the trial.

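### Section 12.2 still promises 330 caregivers and 80% power at each site, but Section 5.3 reports under-enrollment at both sites and fills the whole gap from Ohio, so Washington's stated size and power are unsupported.

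*Combined protocol and SAP*

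**What the plan says.** The Protocol Summary sets the total: "sample size=660 caregivers to be randomized". Section 12.2 makes the primary comparisons "overall and separately for each study site (Ohio and Washington"). It then gives the size per site: "we find that a sample size of 102 per intervention group per site (thus, 306 subjects per site) will provide 80% power" for 19% vs 37% and for 37% vs 57%, with 98% power when the sites are combined. It expects 347 eligible Washington caregivers, based on 85% participation, mentions 5% out-of-school transfers, and concludes: "Thus, we expect to randomize 330 caregivers/site to the five study arms".

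Section 5.3 was updated after the first recruitment year: "Due to lower than expected enrollment in both the Ohio and Washington sites, we plan a second year of recruitment to include Bedford School District". The only other district it names for that year is East Cleveland. Bedford is projected from year-1 experience at 60% participation, "taking into account 30% multiple children and 50% caries rate", which gives 267 caregivers; East Cleveland adds about 50. Then: "Of the 950 screened we expect to randomize 317 caregivers". The section concludes from this: "So we can meet our recruitment goal of 258 caregivers that is necessary to complete the study". Table 4.1.1 places both districts in Cuyahoga County, Ohio. Section 5.3 describes no year-2 recruitment in Cowlitz or Lewis County.

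Under Section 12.4, a treatment comparison that is significant overall is then tested within each site at 0.05.

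**The concern.** The two sections describe different trials. Section 12.2 describes two equal sites of 330, each powered on its own. Section 5.3 describes a trial that fell short at both sites and will be completed in Ohio. If Washington stopped below 330, its number stays there, and the 80% in Section 12.2 does not apply to it. Section 12.2 is also out of date for Ohio: it still builds that pool from 889 children, East Cleveland's enrollment alone, without Bedford's 1,274.

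What is at stake is how a Washington result is read. If standard letter vs CSM letter, or CSM letter vs CSM letter plus DIG, is significant overall but not in Washington, a reader who relies on the stated 80% would take that as fair evidence of no effect at the rural site. With fewer caregivers, it could simply reflect low power.

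**Working it through.** **Inputs.** From Section 12.2: rates 19%, 37% and 57%; two-sided pooled-variance Z test at 0.05; 5% transfers. From Section 5.4.1: allocation 17:17:2:2:17, so a main arm is 17/55 of those randomized. From Section 5.3: 258 needed, 317 expected. From the Protocol Summary: 660 in total.

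**Formula.** With n per arm and p̄ = (p1 + p2)/2,

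power = Φ{ [ |p1 − p2|√n − 1.96√(2p̄(1 − p̄)) ] / √(p1(1 − p1) + p2(1 − p2)) }.

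**Reproducing the plan.** 330 × 17/55 = 102 per main arm. For 19% vs 37%: (0.18 × 10.100 − 1.96 × 0.635)/0.622 = 0.92, so power is 82.2%. For 37% vs 57% it is 82.1%. After 5% loss, n = 96.9 and power is 80.2% and 80.1%. With 204 per arm it is about 98%. The stated figures follow from their inputs.

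**Slack.** 80% for both contrasts needs a site total of 313 with no loss (96.7 per arm), or 329 if 5% are lost after randomization (96.6 per arm). The 330 is 306 plus 24 for the two reduced arms, so it adds no drop-out reserve to the main arms.

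**Section 5.3.** 1274 × 0.60 = 764; 764 × 0.50 × 0.70 = 267; 267 + 50 = 317. The sums are right, and every one of these caregivers is in Ohio. Assuming that 258 is measured against 660, year 1 randomized 660 − 258 = 402 over both sites. Washington then reaches 330 only if Ohio randomized 402 − 330 = 72 in year 1, against an expected pool of 366.

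**Power at illustrative Washington totals** (not counts from the documents), 19% vs 37%; 37% vs 57% agrees within 0.1 point:

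| Washington total | No loss | After 5% loss |
|---|---|---|
| 330 | 82.2% | 80.2% |
| 300 | 78.4% | 76.3% |
| 250 | 70.6% | 68.4% |
| 200 | 60.8% | 58.6% |

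For 19% vs 57%, power is 97.5% (96.9% after loss) even at 150.

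**Siblings.** Section 12.2 calls its caregiver count conservative, and Section 12.4 analyses children by GEE. If a fraction s of caregivers has two eligible children with correlation ρ, the effective number per caregiver is k = (1 − s) + 2s/(1 + ρ). Take ρ = 0.5, an assumption.
- s = 0.10 (Section 12.2): k = 1.033; the 80% threshold after 5% loss is 319; power at 200, 250 and 300 is 60.0%, 69.8% and 77.6%.
- s = 0.43 (from Bedford: 764 × 0.50 = 382 positive children, 382/267 = 1.43 per caregiver): k = 1.143; the threshold is 288; power is 64.4%, 74.2% and 81.7%.

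**IPQ-RD, separate from enrollment.** Section 12.2 states 80% per-site power for 10 points with SD 27, and names no test. At 102 per arm a two-sided unadjusted t-test gives 74.9%; 80% needs 116 per arm or a 10.6-point difference. A one-sided test gives 83.9%. A two-sided test reaches 80% if baseline covariates correlate about 0.34 with the outcome.

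**The case against.** Section 12.2 makes a conditional statement, that 102 per arm gives 80% power, and it is true. No Washington count is reported. Enrollment in Section 4.1 means signing consent and completing the contact form, so low enrollment does not prove a shortfall in randomized caregivers. The year-2 wording may not be a complete list of districts. The 5% may also have been taken before randomization: 347 × 0.95 = 329.65, close to 330. On that reading the relevant threshold is 313, not 329, and there is more room. Overall power is intact, and a Washington result will come with its own model, confidence interval and site-by-intervention test. On the IPQ-RD, Section 12.4 plans regression with baseline covariates, so 75% is one unadjusted figure.

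Most of this limits the size of the point, and it stands to that extent: the shortfall is unknown, and the totals of 200 to 300 are only illustrations. The 5% is ambiguous, since Section 5.5.1 lists transfer out of the district as a reason for ending participation, which supports loss after randomization. None of this reconciles the two sections. Section 12.2 goes beyond a conditional statement when it expects 330 at each site, and Section 5.3 fills the entire remaining goal from Ohio. If Washington does recruit in year 2, one sentence would settle it.

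**Conclusion.** The point holds. The size and power stated for Washington in Section 12.2 are not supported by the recruitment plan in Section 5.3, and they bear on a comparison listed among the primary aims. This should be fixed. The documents do not show what Washington's power is; they show that 80% cannot be taken as given. A total of 300 would give about 76 to 78% and a total of 200 about 59 to 61%, at caregiver level. Sibling data could raise the after-loss figures to at most about 82% and 64% under the assumed correlation of 0.5.

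The exposure is confined to the two smaller contrasts at Washington. Combined power stays at 98% if 660 is reached, and the 19% vs 57% comparison keeps about 97% or more down to 150 caregivers. The per-site IPQ-RD power of 80% is overstated by about 5 points unless a one-sided test or covariate adjustment was intended.

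**What to change.** In Section 12.2, replace the 330 per site and the 80% per-site power with the actual year-1 randomizations and projected final numbers for each site, and say whether Washington recruits in year 2. From those numbers, restate per-site power for 19% vs 37% and 37% vs 57% under the existing caregiver-level convention, after 5% transfers, and say whether the 5% falls before or after randomization. Keep the remark that sibling data may add some power. The thresholds 313 and 329 are checks and should not be written in as rules.

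In the same revision, change the per-site IPQ-RD power to about 75%, or name the test and covariate adjustment that give 80%.

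Section 12.4 needs no change. The fix is wording in Section 12.2 only, with no extra participants and no change to the analysis. The cost is a possibly less favourable stated power for Washington.

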5.4 Treatment Assignment Procedures

5.4.1 Randomization Procedures

Sequence Generation: The study Biostatistician will generate the randomization sequence, which will be loaded into REDCap for allocation. REDCap is a secure, web-based application designed to support remote data capture for research studies, providing: 1) an intuitive interface for validated data entry, 2) audit trails for tracking data manipulation and export procedures, 3) automated export procedures for seamless data downloads to common statistical packages, and 4) procedures for importing data from external sources. Caregivers will be randomly assigned to one of the five study arms in the 17:17:2:2:17 ratio; randomization of caregivers will be stratified by their child's grade level and school. The caregivers with multiple children will receive the same treatment based upon the grade level and school of one of their children, selected at random. Permuted blocks will be used to ensure the allocation of treatment assignments within strata as planned. Only the Biostatistician and the Data Manager will be aware of the blocking scheme and the actual assignments.

Allocation Process: Caregivers will be allocated to study arms using the randomization module provided in REDCap. REDCap uses previously-generated randomization sequences to assign records to study arms, and can support up to 14 stratifying variables. Each unique caregiver ID will be linked to one or more unique child IDs in a one-to-many relationship. As each child record is examined, the corresponding caregiver's study arm assignment will be displayed. If no allocation is found, the study staff will be directed to the randomization form to allocate that caregiver to the correct arm. REDCap will assign each caregiver to a specific study arm in accordance with the pre-determined randomization sequence and the stratifying variables. To assist study staff in quickly processing randomizations, stratifying variables (as well as other basic data) will be prepopulated into REDCap by the Project Coordinators, using information gathered prior to the dental screening and randomization process. REDCap is secured using TLS/SSL, enabling study staff to use it from laptops using public or private wireless connections.

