4 STUDY DESIGN

This section describes the model and design of the intervention study. The study will utilize a multi-site, double-blind, parallel arm, community-based randomized trial design (Phase 3).

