5.4.2 Masking Procedures

All personnel who have contact with the child and caregiver will be blinded to participant group assignment except for personnel on the Data & Statistics Team. In order to maintain blinding, the dental examiners will not have access to study arm allocation.

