14.2 Study Intervention and Study Questionnaires

Quality Assurance Procedures

The **Outreach Workers and study staff**, who will facilitate the receipt of intervention letters and access to the study questionnaires, will attend a 2-day in person training on the conduct of the study protocol and logistics (See MOP Section 5). In-class training will incorporate the topics of human subject protection, Good Clinical Practice (GCP), and the study protocol. A segment of the training will emphasize how data management procedures promote high-quality data collection and reduce threats to fidelity. Focus will be placed on following the procedures that have been outlined in the protocol, principles of data management, and forms administration procedures. All types of documentation will be discussed including forms filled out by participants and study forms completed by staff. For each, the purpose, instructions for completion and procedures to maintain accuracy will be addressed. As part of tracking and managing study records, staff members will learn how to document activities that occur with subjects, update study documentation, and use the tracking logs. As part of the training, the study staff will be certified in the topics presented to ensure their comprehension of the expectations.

Fidelity of the **Outreach Workers'** telephone contacts with caregivers will be assessed throughout the study to ensure that they have not provided additional information to the childrens' caregivers that might influence the outcome. (Refer to MOP Section 5).

For reliability purposes and to further assess the stability of the IPQ-RD presumably after visits to the dentists (between 2 and 4 weeks), we will randomly select a sub-sample of 60 caregivers (20 each in arms 1, 2, and 4) to respond to the IRQ-RD after 4 weeks.

Quality Control Procedures

The first ten (10) **Outreach Workers** telephone contacts (reminder calls to return the questionnaires) will be audio recorded in digital media and reviewed. Then, the first ten (10) of the following remaining type of call will be recorded and reviewed for each Outreach Worker (confirmation of receipt of referral letters-calls #2, and reminders to return completed questionnaires-calls #4 and #6). At the beginning of the study, the **Project Coordinators** will review the first ten telephone contacts to ensure fidelity of the calls and accuracy of data recording.

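### Section 5.4.1 shows the study arm to unspecified study staff, against its own two-role limit and, unless they sit on the Data & Statistics Team, against the blinding rule in 5.4.2

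*Combined protocol and SAP*

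**What the plan says.** Section 4 labels the trial double-blind without naming the blinded parties. Three statements then govern who may know the arm.

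- Section 5.4.1, in the paragraph on generating the sequence: "Only the Biostatistician and the Data Manager will be aware of the blocking scheme and the actual assignments".
- Section 5.4.1, in the next paragraph, on allocation in REDCap: "As each child record is examined, the corresponding caregiver's study arm assignment will be displayed". It continues: "If no allocation is found, the study staff will be directed to the randomization form to allocate that caregiver to the correct arm". It describes the system as "enabling study staff to use it from laptops using public or private wireless connections".
- Section 5.4.2: "All personnel who have contact with the child and caregiver will be blinded to participant group assignment", with one exception: "except for personnel on the Data & Statistics Team". It adds that dental examiners have no access to the allocation.

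On delivery, section 6.3 makes the Project Coordinator at each site responsible for seeing that letters go out and for supervising the Outreach Workers. Section 6.4 has an Outreach Worker telephone each caregiver to confirm receipt and, if the letter did not arrive, send another. Sections 6.2 and 6.4 confirm that Arms 2 and 4 also receive a dental information guide.

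**The concern.** Read in sequence, section 5.4.1 first restricts the assignments to two people and then describes a screen on which study staff see them. Section 5.4.2 tells the reader that people who deal with families do not know the arm, yet no step keeps the arm from those who allocate, pack or resend the letters.

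This matters because the primary outcome requires a caregiver to act. Section 12.2 counts restorations or extractions that appear between the two exams, so a caregiver must have taken the child to a dentist. Outreach Workers are recruited locally partly for their rapport with caregivers (section 5.3), and they telephone families several times. The plan itself recognises the route: section 14.2 reviews their calls to "ensure that they have not provided additional information to the childrens' caregivers that might influence the outcome". A worker who knows the arm could encourage some families more than others, and the resulting difference would be credited to the letter.

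**Working it through.** No formula applies to the main point, so the check sets the passages side by side.

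1. **Within 5.4.1.** One sentence limits the actual assignments to two roles. The next paragraph displays the arm and has study staff operate the form. Taken literally, both cannot hold.

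2. **5.4.1 against 5.4.2.** The conflict disappears if the staff at the screen are all on the Data & Statistics Team. Nothing says that they are, and three places point the other way. Section 16.4 lists that team separately from the principal investigators, Project Coordinators and other study staff. Section 14.2 gives data entry to the Project Coordinators at each site and puts the team, in a monitoring role, at CWRU. Section 5.4.1 has Project Coordinators pre-load the stratifying variables. The conflict is therefore likely but conditional.

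3. **Where the screen is used.** Section 7.2 lists randomization under the baseline screening visit, section 4.2 sends the letter home that same day, and section 5.4.1 speaks of laptops on wireless connections. Use near the schools, including in Washington, is a fair inference. It is not stated.

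4. **The resend step.** To send the correct replacement, an Outreach Worker must either know the arm or be handed a closed packet. The documents mention packets but not that they are closed, numbered or prepared by someone else.
   - Caregivers due to receive a guide (Arms 2 and 4): 204 + 24 = 228 of 660, or 228/660 = 34.5%. An open packet shows at once whether a guide is inside, and the letter text differs as well.
   - Section 6.2 reports that in the pilot 25% had not received a letter sent by both routes. If that rate recurred and all such caregivers were reached, resends would number about 0.25 × 660 = 165. This shows how often the route could be used. It does not measure bias.

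5. **Later contact.** The receipt call allows five attempts (section 6.4), and reminder calls follow at two weeks and at the end (sections 7.3 and 7.4). The call content that is reviewed is the first ten calls of each listed type (sections 6.3 and 14.2).

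6. **Who is not exposed.** Examiners are barred from the allocation (5.4.2), and the follow-up examiner does not see the baseline findings (3.2.1). No passage discloses the arm to caregivers.

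**The case against.** The strongest reply has four parts.

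- The two-role sentence sits under sequence generation and may refer only to the pre-generated list. That is a possible reading, and it would soften step 1. It leaves steps 2 and 4 untouched.
- Section 5.4.2 expressly allows an unblinded team, and 5.4.1 does not say who the study staff are. This stands, and it is why the conflict with 5.4.2 is stated as conditional.
- No passage has Outreach Workers operating the allocation screen; they pass completed forms to the sites for data entry (14.2). Every letter carries the same generic code, so reading it out on the receipt call does not reveal the arm (6.4). Calls are scripted, early calls of each type are reviewed, and all contacts are logged and reviewed (6.3). These are real safeguards, and they narrow the exposure. They do not cover the resend step, where the worker handles the letter.
- The Manual of Procedures, which was not available, may specify roles, coded displays or sealed packets. If so, the protocol still needs to agree with it.

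A reader might go further and infer that the double-blind design fails. The documents do not support that: outcome assessment stays masked and caregivers are not told their arm. A reader might also infer that the arm appears on screen during the dental exam itself. The wording about examining a record most naturally means opening it in REDCap, and examiners are denied access in any case. Nor does a sibling's shared arm add a problem: sharing is by design, and the examiner scoring the sibling cannot see it.

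**Conclusion.** The point holds in a limited form. Section 5.4.1 exposes the arm to staff it does not identify. That conflicts with its own two-role limit on the plain reading, and with 5.4.2 if any of those staff have contact with families and are outside the Data & Statistics Team. Separately, section 6.4 has a role that should be blinded send arm-specific material with no stated concealment.

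The consequence is a risk of performance bias through staff contact with caregivers. It is not detection bias. The documents contain no figure for how much staff encouragement changes dental attendance, so any percentage-point effect would be invented, and none is offered. The conclusion assumes that the Manual of Procedures does not already close the gap. The change is worth making because the outcome is caregiver behaviour and the remedy is cheap.

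**What to change.** - Restrict the REDCap allocation field to the Data & Statistics Team.
- Show all other staff only a packet number that is unique to each caregiver. A code shared by everyone in an arm would be deciphered quickly.
- Have that team pre-pack the letter, with the guide where applicable, in opaque numbered envelopes, plus a spare under the same number for resends. Coordinators and Outreach Workers then send packets without seeing the contents. Because a guide can be felt through paper, the team should check that packets cannot be told apart by thickness. The language of the letter can be marked outside, since it does not reveal the arm.
- Rewrite 5.4.1 and 5.4.2 to agree: name the roles that may see the arm, and state in 6.4 how a replacement is sent without revealing it.

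The cost is a change of REDCap access rights and extra packing before screening, including spares and both languages where needed. No additional staff are required. Section 5.3 plans a second recruitment year, so the change could apply at least from then.

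If the Manual of Procedures already contains these steps, only the wording of the protocol needs to change.
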